# 4.1.2.3 General Safety Exclusion Criteria:

Patients who meet any of the following safety-related criteria will be excluded from the study:

- Any surgical procedure (except for non-ophthalmic minor surgeries\*) within 4 weeks prior to screening
- Planned surgical procedure (except for non-ophthalmic minor surgeries\*) during the study
  - \* Note: A minor surgical procedure is considered a procedure that requires only local anesthesia or conscious sedation (does not require general, neuraxial or regional anesthesia) and is done on an ambulatory/outpatient basis (e.g., toenail surgery, mole surgical excision, wisdom tooth extraction).

Note: All ophthalmic surgical procedures, major or minor, including strabismus surgeries, are prohibited within 4 weeks prior to screening and should not be planned during the study.

- Evidence of progressive multifocal leukoencephalopathy
- Evidence of serious uncontrolled concomitant diseases that may preclude patient participation, such as other nervous system disease, cardiovascular disease, hematologic/hematopoiesis disease, respiratory disease, muscular disease, endocrine disease, including thyroid disease, renal/urologic disease, digestive system disease
- Congenital or acquired immunodeficiency, including HIV infection

- Active or recurrent bacterial, viral, fungal, mycobacterial infection, or other infection (excluding fungal infection of nail beds or dental caries) at baseline
- Infection requiring hospitalization or treatment with IV anti-infective agents within 4 weeks prior to baseline visit or oral anti-infective agents within 2 weeks prior to baseline visit
- Positive screening tests for hepatitis B, defined as either of the following:
  - o Positive hepatitis B surface antigen [HBsAg]
  - Positive total hepatitis B core antibody [total HBcAb] confirmed by a positive viral DNA PCR
- Positive screening test for hepatitis C (defined as positive hepatitis C virus [HCV] antibody and detectable HCV RNA)

Participants with positive HCV antibody and undetectable HCV RNA 12 weeks after HCV treatment completion are eligible to participate in the study.

- History of drug or alcohol abuse within 1 year prior to baseline
- History of diverticulitis or concurrent severe GI disorders (such as symptomatic diverticulosis) that, in the investigator's opinion, may lead to increased risk of complications such as GI perforation

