# 4.5.2.2 Hepatitis C Screening

Patients with negative hepatitis C serology can be enrolled. Patients with positive hepatitis C serology will be excluded from the study. However, if HCV RNA is undetectable ≥ 12 weeks after HCV treatment completion, the patient can be enrolled.

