# 4.5.6 Laboratory, Biomarker, and Other Biological Samples

Samples for the following laboratory tests will be sent to the central laboratory for analysis. Instruction manuals and supply kits will be provided for all central laboratory assessments.

- Hematology: WBC count, RBC count, hemoglobin, hematocrit, platelet count, and absolute differential count (neutrophils, eosinophils, basophils, monocytes, lymphocytes, other cells)
- Coagulation: INR and fibrinogen
- Serum chemistry: sodium, potassium, chloride, calcium, phosphorous, ferritin, BUN, creatinine, total bilirubin, total protein, albumin, ALT, AST, ALP, gamma-glutamyl transpeptidase, lactate dehydrogenase, CRP, CK, lipase, and uric acid
- Lipids: total cholesterol, LDL cholesterol, HDL cholesterol, and triglycerides
- Quantitative immunoglobulins: IgA, IgG, IgM, and IgE
- IgG subclass (IgG1, IgG2, IgG3 and IgG4)
- T-, B- (defined by CD19+) and natural killer cells (TBNK panel)
- Complement C3, C4 and CH50
- Screening for HBV infection: HBsAg, total HBcAb, and (if HBsAg test is negative and total HBcAb test is positive) HBV DNA.
- Screening for HCV infection: HCV antibody and (if HCV antibody test is positive) HCV RNA. If a patient has a positive HCV antibody test at screening, an HCV RNA test must also be performed to determine if the patient has an HCV infection.
- Serum pregnancy test at screening

Samples for the following laboratory tests will be sent to the study site's local laboratory for analysis:

 Urinalysis (urinary glucose, urinary protein, urinary occult blood, urobilinogen) will be conducted at each site by dipstick. If any abnormalities are detected on urine dipstick tests, a complete urinalysis (including microscopic of examination of urine) and/or urine culture is to be performed (at local laboratory) as deemed necessary.

- Interferon Gamma Release Assay as part of TB screening
- Cortisol and low-dose ACTH stimulation test (if deemed necessary after Week 12 of the OLE period)
- Pregnancy test:

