- HBsAg, HBcAb, HBsAb, HCVAb: All patients must have negative HBsAg test result at screening prior to enrollment. Hepatitis B screening: Patients who are HBsAg positive will be excluded from the study. If HBcAb status is positive, hepatitis B viral DNA will be measured. If HBV DNA is detectable, the individual must be excluded. If HBV DNA is undetectable, the individual may be enrolled. In these participants, HBV DNA measurement must be performed regularly at 12 weekly intervals during the study. Hepatitis C screening: If HCVAb is positive, HCV RNA will be measured. If HCV RNA is undetectable ≥12 weeks after HCV treatment completion, the patient can be enrolled.
- w Quantitative immunoglobulins may include lgA, lgE, lgG, and lgM. ™
- x IgG subtypes include IgG1, IgG2, IgG3 and IgG4.
- Medication (e.g., prescription drugs, over-the-counter drugs, vaccines, herbal or homeopathic remedies, nutritional supplements) used by a patient in addition to protocol-mandated treatment.

- z All adverse events will be reported for as long as the patient remains in the study. Serious adverse event reporting starts with signing of the Informed Consent Form. The investigator should follow each adverse event until the event has resolved to baseline grade or better, the event is assessed as stable by the investigator, the patient is lost to follow up, or the patient withdraws consent. Every effort should be made to follow all serious adverse events considered to be related to study drug or to trial-related procedures until a final outcome can be reported.
- aa Efficacy assessments must be performed prior to dosing and prior to any other assessments, preferably at the same time in the morning across all visits.
- bb These assessments only apply to RLD Visits 1 and 3.
- cc PD biomarkers will include, but are not limited to, IL-6 and sIL-6R.
- dd RNA may be assessed for exploratory biomarkers including, but not limited to, plasmablast signature.
- ee For adolescent patients at the time of informed consent, this sample is not to be collected.
- ff Blood samples will be processed for flow cytometry (e.g., B-cell subsets).
-  Autoantibodies will include AChR, MuSK and LRP4. *Note that for sites in the Netherlands and Germany, the central laboratory autoantibody tests at screening to confirm gMG diagnosis are not required.*

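### Protocol Sections 4.1.2.3 and 4.5.2.2 contradict each other on HCV antibody-positive, RNA-undetectable patients who never had HCV treatment, and leave those under 12 weeks after treatment ambiguous

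*Protocol*

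**What the plan says.** Six places in the protocol bear on hepatitis C eligibility.

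- **Section 4.1.2.3 (general safety exclusion criteria)** gives the exclusion as "Positive screening test for hepatitis C (defined as positive hepatitis C virus [HCV] antibody and detectable HCV RNA"). A note beneath it adds: "Participants with positive HCV antibody and undetectable HCV RNA 12 weeks after HCV treatment completion are eligible to participate in the study".
- **Section 4.5.2.2 (hepatitis C screening)** allows enrolment with negative serology and then states: "Patients with positive hepatitis C serology will be excluded from the study". Its one exception follows: "However, if HCV RNA is undetectable ≥ 12 weeks after HCV treatment completion, the patient can be enrolled".
- **Section 4.5.6 (laboratory samples)** makes RNA the follow-up test that decides whether there is infection; the sentence begins: "If a patient has a positive HCV antibody test at screening, an HCV RNA test must also be performed to determine if the patient has".
- **Appendix 1, hepatitis test footnote**, sends antibody-positive patients to an RNA test and then says: "If HCV RNA is undetectable ≥12 weeks after HCV treatment completion, the patient can be enrolled". The matching footnote in **Appendix 2**, which governs screening of adolescents who enter the open-label extension directly, says the same.
- **Section 5.1.1.1 (infections)** restates that positive hepatitis B or C screening tests exclude, and refers back to Section 4.1.2.

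**The concern.** The two main sections start from different defaults. Section 4.1.2.3 does not exclude an antibody-positive patient unless RNA is detectable. Section 4.5.2.2 excludes an antibody-positive patient unless the post-treatment exception is met. Someone who satisfies neither the 4.1.2.3 definition nor the 4.5.2.2 exception gets an answer that depends on which page the site reads.

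This matters for two reasons. These are safety eligibility criteria for an IL-6 receptor blocker, often given on top of immunosuppressants. And Section 9.2 bars prospective waivers of eligibility criteria, while Section 6.2 of the protocol and Section 4.6.2 of the SAP require major deviations to be listed and evaluated. With two rules in force, the same enrolled patient can be compliant under one section and a deviation under the other.

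**Working it through.** No sample size, power or error-rate figure is involved, and the plan states no number to reproduce. The check is to apply each section's wording to every relevant combination of antibody status, RNA status and treatment history. The note in Section 4.1.2.3 is read as meaning at least 12 weeks, to match Section 4.5.2.2.

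| Case | Antibody | RNA | HCV treatment | Section 4.1.2.3 | Section 4.5.2.2 | Result |
|---|---|---|---|---|---|---|
| 1 | Negative | n/a | any | Not excluded | Can be enrolled | Agree |
| 2 | Positive | Detectable | any | Excluded | Excluded | Agree |
| 3 | Positive | Undetectable | Completed at least 12 weeks ago | Eligible (note) | Can be enrolled | Agree |
| 4 | Positive | Undetectable | Never | Not excluded | Excluded | **Contradiction** |
| 5 | Positive | Undetectable | Completed less than 12 weeks ago | Definition does not exclude; note implies a 12-week wait | Excluded | **Ambiguous** |

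**Case 4** could be, for example, an infection cleared without therapy or a false-positive antibody result. The 4.1.2.3 definition fails because RNA is not detectable, and the note is silent because it concerns treated patients. In 4.5.2.2 the serology is positive, so the default excludes, and an exception counted from treatment completion cannot be met by someone with no treatment to complete.

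**Case 5** turns on the note. It says who is eligible, not who is excluded, so it does not alter the definition. It would nevertheless have little purpose if shorter intervals were also acceptable.

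The other places do not settle either case. Section 4.5.6 uses RNA to determine infection, which fits 4.1.2.3 but is not an eligibility rule. The Appendix 1 and 2 footnotes name only the post-treatment case as enrollable and say nothing about untreated patients. Section 5.1.1.1 sends the reader back to 4.1.2.

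The hepatitis B text is a useful comparison. Sections 4.1.2.3 and 4.5.2.1 give the same answer there: core-antibody positivity with detectable viral DNA excludes, and with undetectable DNA it does not. Only hepatitis C has two defaults.

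**The case against.** The strongest reply is that failing to meet one exclusion criterion is not a declaration of eligibility. Section 4.5.2.2 is a further explicit condition, and a site that follows the whole protocol would apply both sections and exclude cases 4 and 5. That reading is available, but the protocol does not state it. It would also leave the 4.1.2.3 definition with no work to do, because every patient it excludes already has positive serology and detectable RNA and so is excluded under 4.5.2.2. The reply weakens the practical risk; it does not reconcile the text.

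Three broader readings might be inferred, and the documents do not support them.

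- **That the sections disagree for antibody-positive, RNA-undetectable patients as a group.** They do not. Both admit those at least 12 weeks past completed treatment (case 3).
- **That a patient still taking HCV therapy slips through Section 4.1.2.3.** The same list excludes infection requiring oral anti-infective agents within 2 weeks before baseline, or intravenous agents within 4 weeks. On its face this catches a patient still on oral antivirals. For oral therapy, case 5 is therefore mainly a window from about 2 to 12 weeks after completion.
- **That case 5 is a flat contradiction that lets a patient through.** Enrolling such a patient would mean disregarding both the note and Section 4.5.2.2. Section 4.1.2.3 also has a general exclusion, on the investigator's judgment, for serious conditions or laboratory abnormalities that preclude safe participation. Ambiguous is the fair description.

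The objection that little prospective effect remains also stands. SAP Section 1.2.3 says adult screening has stopped, and adolescents enrolled after the last adult was randomized do not contribute to the primary analysis.

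**Conclusion.** The point holds in a narrow form. There is one clear contradiction (antibody positive, RNA undetectable, never treated) and one ambiguity (RNA undetectable, off treatment, less than 12 weeks from completion). The sections agree in the other three cases.

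The size cannot be computed. The documents give neither the prevalence of HCV antibody in this population nor the number screened. Any count of antibody-positive patients would in any case overstate the problem, because it would include those on whom the sections agree. The number affected is likely very small and may be zero.

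No efficacy estimate, power figure or error rate depends on this. The deviation types that SAP Section 4.2.4.2 singles out for sensitivity analysis do not include hepatitis eligibility. What is affected is the consistency of eligibility decisions for adolescents still being screened, and the classification of any such patient already enrolled. It is a minor point, but the text is contradictory as written rather than merely short of detail. The conclusion rests on a literal reading of the sections and takes no position on which rule is right.

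**What to change.** Reconcile Section 4.1.2.3, Section 4.5.2.2 and the hepatitis footnotes in Appendices 1 and 2 to a single eligibility statement, and align Sections 4.5.6 and 5.1.1.1 with it. The statement should give an explicit answer for antibody-positive patients in each of three situations:

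1. RNA detectable.
2. RNA undetectable after completed HCV treatment, by time since completion.
3. RNA undetectable with no HCV treatment.

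The sponsor's clinical team should decide the content of each answer. Use the agreed statement to classify deviations, including for patients already enrolled.

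The cost is protocol wording. HCV antibody and follow-up RNA tests are already performed at screening, so no new sample or assay is needed, and no change to the SAP's analyses follows.

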#### 4.1.2.4 Laboratory Exclusion Criteria (at Screening):

Patients who have any of the following laboratory abnormalities at screening will be excluded from the study:

- WBC  $< 3.0 \times 10^{3}/\mu L$
- ANC  $< 2.0 \times 10^3 / \mu L$
- Absolute lymphocyte count < 0.5 × 10^3/μL
- Platelet count < 10 × 10^4/μL
- AST or ALT > 1.5 × upper limit of normal (ULN)

If retest is conducted because the initial result meets an exclusion criterion, it must be conducted at a central laboratory and the last value obtained determines the patient's eligibility for randomization/ $Day\ 1$ , otherwise local laboratory can be used.

### 4.2 METHOD OF TREATMENT ASSIGNMENT AND BLINDING

Randomization and blinding will be employed to minimize bias in treatment assignment *in the DB period* and to provide the basis for valid statistical inference.

#### 4.2.1 Treatment Assignment

This is a randomized, DB study (except for adolescent patients enrolled directly in the OLE period of the study). After initial written informed consent has been obtained, all screening procedures and assessments have been completed, and eligibility has been established for a patient, the study site will obtain the patient's identification number and treatment kit assignment from an interactive voice or web-based response system (IxRS).

Patients will be randomly assigned to one of two treatment groups: placebo or satralizumab. Eligible patients must be randomized through the IxRS prior to receiving any study drug. Randomization will occur in a 1:1 ratio through use of a permuted-block randomization method to ensure a balanced assignment to each treatment group. Randomization will be stratified according to the following criteria:

- Baseline SOC treatment: AChEI monotherapy and/or an OCS versus a steroidsparing IST monotherapy or a combination of steroid-sparing IST with other treatments (an AChEI and/or an OCS)
- Autoantibody type: AChR positive versus AChR negative (includes MuSK gMG and LRP4 gMG)
- Region: North America versus Europe versus rest of world

Adolescent patients enrolled in the study will directly enter the OLE period after completion of screening and receive open-label satralizumab. For information on adolescents that have been enrolled through previous versions of the protocol (prior to global protocol Version 5), refer to Section 3.1.3.

The lxRS system will also take into account patients' weight at baseline to allocate to the correct dose.

# 4.2.2 Blinding

Study site personnel and patients will be blinded to treatment assignment during the study. The Sponsor and its agents will also be blinded to treatment assignment, with the exception of individuals who require access to patient treatment assignments to fulfill their job roles during a clinical trial. These roles include the unblinding group responsible, clinical supply chain managers, central laboratory sample handling staff, operational assay group personnel, IxRS service provider, and iDMC members.

To maintain integrity of the trial results and to prevent potential unblinding of the assigned group during the DB treatment phase as a result of adverse events or changes to laboratory results, the following additional measures will be implemented until the time of the primary analysis:

To prevent potential unblinding as a result of adverse events or laboratory changes, a "dual assessor" approach will be used to evaluate efficacy and safety. Each site will have two separate investigators: a treating investigator and a rating or examining investigator.

The **treating investigator** will be the safety assessor and should be a neurologist with experience in the care of patients with MG. The Treating Investigator will have access to all patient data and will make all treatment decisions on the basis of a patient's clinical response and laboratory findings. This role may be conducted by the principal investigator.

The examining investigator will be the efficacy assessor and should be a qualified HCP trained and experienced in administering and scoring the MG-ADL, QMG, and MGC. The examining investigator (or designee, fulfilling the same criteria) will complete the QMG and MGC assessments. During the DB treatment period, the examining investigator and his or her qualified designees (if applicable) will not be involved with any aspect of medical management of the patient and will not be allowed access to patient data. The roles of the treating and examining investigator need to be documented in the Investigator's Site File for each patient. The treating investigator and the examining investigator should not switch roles for a specific patient. It is recommended that the same examining investigator assesses a specific patient throughout the DB treatment period. This role cannot be conducted by the principal investigator.

The dual assessor approach should be applied until the database lock for the primary analysis for the study has been achieved.

- Patient education: During the DB treatment period, prior to being examined by the
  examining investigator, patients should be instructed not to discuss with the
  examining investigator what (if any) adverse effects they may be experiencing.
- Blinding of laboratory parameters: Selected laboratory parameters that may lead to unblinding of the treatment assignment, such as fibrinogen, CRP, immunoglobulins, and complement levels, will be blinded until the primary analysis is complete. The iDMC will perform periodic unblinded safety reviews, which include the blinded laboratory parameters.

While PK and immunogenicity samples must be collected from patients assigned to the placebo group to maintain the blinding of treatment assignment, PK and ADA assay results for these patients are generally not needed for the safe conduct or proper interpretation of the study data. Laboratories responsible for performing study drug PK and ADA assays will be unblinded to patient treatment assignments to identify appropriate samples for analysis. PK samples from patients assigned to the placebo group will not be analyzed for study drug PK concentration except by request (e.g., to evaluate a possible error in dosing). Baseline immunogenicity samples will be analyzed for all patients. Post-baseline immunogenicity samples from patients assigned to the placebo group will not be analyzed for ADAs except by request.

If unblinding is necessary for a medical emergency (e.g., in the case of a serious adverse event for which patient management might be affected by knowledge of treatment assignment), the investigator will be able to break the treatment code by contacting the IxRS. The treatment code should not be broken except in emergency situations. The investigator is not required to contact the Medical Monitor prior to breaking the treatment code. However, the investigator should inform the Medical Monitor that the treatment code has been broken.

If the investigator wishes to know the identity of the study drug for any reason other than a medical emergency, he or she should contact the Medical Monitor directly. The investigator should document and provide an explanation for any non-emergency unblinding. If the Medical Monitor agrees to patient unblinding, the investigator will be able to break the treatment code by contacting the lxRS.

As per health authority reporting requirements, the Sponsor's Drug Safety representative will break the treatment code for all serious, unexpected suspected adverse reactions (see Section 5.7) that are considered by the investigator or Sponsor to be related to study drug. The patient may continue to receive treatment, and the investigator, patient, and Sponsor personnel, with the exception of the drug safety representative and personnel who must have access to patient treatment assignments to fulfill their roles (as defined above) will remain blinded to treatment assignment.

# 4.3 STUDY TREATMENT AND OTHER TREATMENTS RELEVANT TO THE STUDY DESIGN

The investigational medicinal product (IMP) for this study is satralizumab. Background therapy and rescue therapy are considered *auxiliary medicinal products* (*AxMPs*). *Appendix 15 identifies all IMPs and AxMPs for this study (for use in European Economic Area [EEA]).* 

In this protocol, "study treatment" refers to satralizumab or placebo (assigned in addition to background therapy).

